# 9.1.6. Laboratory Assessments

Laboratory tests for haematology, chemistry and urinalysis will be performed as specified in the Table of Schedule of Assessments.

# 9.1.6.1. Pregnancy Screening

In any woman of childbearing potential, i.e. not > 1 year postmenopausal or surgically sterilized, a urine dipstick pregnancy test will be performed at both screening, and then (urine test) every 4 weeks and end-of-study. If the dipstick test indicates a positive result, an hCG laboratory blood test will be performed to confirm the pregnancy.

A woman of childbearing potential cannot be included in the study if any of the following occurs:

- The urine dipstick pregnancy test indicates a positive result and the pregnancy has been not yet been ruled out by the following β-HCG blood test
- No urine dipstick pregnancy test has been performed at screening
- The urine dipstick pregnancy test indicates a negative result, but early pregnancy (≤ 2 weeks from conception) is suspected by the Investigator based on anamnestic elements
- The urine dipstick pregnancy test indicates a negative result, but a pregnancy is suspected by the Investigator based on clinical elements and cannot be ruled out by further investigation.

If a positive urine dipstick pregnancy test occurs at end-of-study, or if a pregnancy is suspected at any time during the study, an hCG blood test will be performed to confirm the pregnancy.

# 9.1.6.2. Eastern Cooperative Oncology Group (ECOG) Performance Status

The investigator or qualified designee will assess ECOG status at screening, prior to the administration of each dose of trial treatment and as specified in the Table of Schedule of Assessments.

# 9.2. Adverse and Serious Adverse Events

#### 9.2.1. Definitions

Definitions regarding safety and pharmacovigilance to be applied in this study are defined below.

#### 9.2.1.1. Adverse Event (AE)

An AE is defined as any untoward medical occurrence in a patient or clinical investigation subject administered a pharmaceutical product and which does not necessarily have to have a causal relationship with this treatment. An adverse event (AE) can therefore be any unfavourable and unintended sign (including an abnormal laboratory finding, for example), symptom, or disease temporally associated with the use of a medicinal product, whether considered related to the medicinal product.

# 9.2.1.2. Serious Adverse Event (SAE)

A serious adverse event is an AE occurring during any study phase (ie, screening, treatment, or follow-up), that fulfils one or more of the following:

- · Results in death.
- It is immediately life-threatening.

- It requires in-patient hospitalization or prolongation of existing hospitalization (hospitalization should not be considered as an AE (therefore also not an SAE) when it is due to: medical or surgical procedures planned before study entry or due to social or economic reasons.
- It results in persistent or significant disability or incapacity.
- Results in a congenital abnormality or birth defect.
- It is a new cancer (that is not a condition of the study). Although new cancer is not always serious as per regulatory definitions, these should be considered and reported as such, with the seriousness criterion "important medical event".
- It is an important medical event that may jeopardize the patient or may require medical intervention to prevent one of the outcomes listed above. Medical and scientific judgement should be exercised in deciding whether expedited reporting is appropriate in other situations, such as important medical events that may not be immediately life-threatening or result in death or hospitalization but may jeopardize the patient or may require intervention to prevent one of the other outcomes listed in the definition above. These should also usually be considered serious. Examples of such events are intensive treatment in an emergency room or at home for allergic bronchospasm; blood dyscrasias or convulsions that do not result in hospitalization; or development of drug dependence or drug abuse.

# 9.2.1.3. Suspected unexpected serious adverse reaction (SUSAR)

SUSARs are serious adverse reactions that could be related to the IMP and assessed as unexpected based on the applicable encorafenib and binimetinib Investigator's Brochure (IB).

#### 9.2.1.4. Adverse drug reaction (ADR)

All noxious and unintended responses to a medicinal product related to any dose should be considered adverse drug reactions. The phrase "responses to a medicinal products" means that a causal relationship between a medicinal product and an adverse event is at least a reasonable possibility, i.e., the relationship cannot be ruled out.

#### 9.2.1.5. Serious adverse reaction (SAR)

A Serious Adverse Reaction is any adverse reaction that fulfils the criteria of seriousness as defined above, therefore is an adverse reaction which results in death, is life-threatening, requires inpatient hospitalization or prolongation of existing hospitalization, results in persistent or significant disability or incapacity, is a congenital anomaly/birth defect, is a new cancer (that is not a condition of the study) or it is an important medical event that might not be immediately life-threatening or result in death or hospitalisation but might jeopardise the patient or might require intervention to prevent one of the other outcomes listed in the definition above.

# 9.3. Assessment

All assessments of AEs (serious and non-serious) listed below should be recorded on the Adverse Event page of the CRF/eCRF or in the SAE form as appropriate.

# 9.3.1. Causality Assessment

An Investigator who is qualified in medicine must make the determination of relationship to the investigational product for each AE (Related or Unrelated). The Investigator should decide whether, in his or her medical judgment, there is a reasonable possibility that the event may have been caused by the investigational product. If no valid reason exists for suggesting a relationship, then the AE should be classified as "unrelated." If there is any valid reason, even if undetermined, for suspecting a possible cause-and-effect relationship between the investigational product and the occurrence of the AE, then the AE should be considered "related."

# 9.3.2. Expectedness assessment by the sponsors

The 'expectedness' of a serious adverse reaction is assessed in the light of the encorafenib and or binimetinib IB. The expectedness assessment will be performed by Sponsor according the information available in last version of study treatment IB. If information on the expectedness has been made available by the reporting investigator, this should be taken into consideration by Sponsor. If Sponsor disagrees with the investigator's expectedness assessment, both, the opinion of the investigator and the sponsor should be provided with the report.

#### 9.3.3. Severity assessment

Severity of AEs will be assessed according to the CTCAE which provides a descriptive terminology, which can be utilized, for Adverse Event (AE) reporting. A grading (severity) scale is provided for each AE as follows:

Grades: Grade refers to the severity of the AE. The CTCAE displays Grades 1 through 5 with unique clinical descriptions of severity for each AE based on this guideline:

- Grade 1 Mild; asymptomatic or mild symptoms; clinical or diagnostic observations only; intervention not indicated
- Grade 2 Moderate; minimal, local or non-invasive intervention indicated; limiting age-appropriate instrumental Activities of Daily Living (ADL)\*
- Grade 3 Severe or medically significant but not immediately life-threatening; hospitalization or prolongation of hospitalization indicated; disabling; limiting self-care ADL\*\*
- Grade 4 Life-threatening consequences; urgent intervention indicated
- Grade 5 Death related to AE

\*Instrumental ADL refer to preparing meals, shopping for groceries or clothes, using the telephone, managing money, etc.

\*\*Self-care ADL refer to bathing, dressing and undressing, feeding self, using the toilet, taking medications, and not bedridden.

# 9.3.4. Action taken

All AEs should be treated appropriately. Treatment may include one or more of the following: no action taken (i.e. further observation only); study medication temporarily interrupted; study

medication permanently discontinued due to this AE; drug therapy given; non-drug therapy given, surgery, hospitalization, unknown, other.

#### 9.3.5. Outcome

Investigators should follow-up AEs until resolution. The outcome of the AEs should be assessed as follows:

- Recovered/Resolved
- Recovering/Resolving
- Not recovered/Not resolved
- Recovered/Resolved with sequelae
- Fatal
- Unknown

# 9.4. Reporting

# 9.4.1. Reporting an Adverse Event

Adverse events (serious and non-serious) spontaneously reported by the patient and/or in response to an open question from the study personnel or revealed by observation will be recorded during the study at the investigational site. Information about AEs (including SAEs) will be collected from the signing of Informed Consent at least until the end of treatment visit or up to resolution. For each AE, the investigator will evaluate and report the onset (date and time), resolution (date and time), severity, causality, action taken, outcome, and whether it caused the patient to discontinue the study.

#### 9.4.2. Reporting a Serious Adverse Event

Any SAEs considered related to the investigational product and discovered by the Investigator at any time after the study should be reported.

Any SAE must be reported by submitting the completed **initial report** section of the trial-specific SAE form within 24 hours of becoming aware of the event. Submission is done by sending the SAE form by fax or e-mail to

# Serious Adverse Events All serious adverse events must be reported by fax within 24 h to

The SAE outcome must be reported within 2 weeks after initial report by submitting the **follow-up** report (e.g. initial SAE form, updated with follow-up information) to the Pharmacovigilance as above. In case the SAE is reported as ongoing after 14 days, the follow-up report must be submitted again with the final outcome. The originals of the SAE forms (both initial and follow-up reports) are kept at the sites in the Investigator's file. The Pharmacovigilance will forward each individual SAE to the coordinating investigator, supporting coordinating investigators and to Sponsor within one working day. Wherever possible copy of summary of hospitalization, autopsy

reports, and relevant laboratory examinations should be provided. Additional follow-up information, if required or available, should all be faxed to Sponsor within one business day of receipt and this should be completed on a follow-up SAE form and placed with the original SAE information and kept with the appropriate section of the CRF and/or study file.

The Sponsor is responsible for notifying the relevant regulatory authorities of certain events. Investigators will also be notified of all unexpected, serious, drug-related events (7/15 Day Safety Reports) that occur during the clinical study.

All SAEs that occur after any patient has signed the first Informed Consent, until end of treatment visit, whether they are related to the study, must be recorded on forms provided by the Sponsor

# 9.4.3. Reporting Pregnancy

In case of a pregnancy notified after the first dose was received, the patient will not receive the following dose and will be followed after delivery of her child. All initial reports of pregnancies in a patient and pregnancies in partners of male patients included in the study from the screening visit must be reported to the Pharmacovigilance by the Investigator within 24 hours of knowledge of the event, using a Pregnancy Form.

Should a pregnancy occur, it must be reported and recorded on pregnancy form. Pregnancy in itself is not regarded as an AE unless there is a suspicion that an investigational product may have interfered with the effectiveness of a contraceptive medication.

Any pregnancy-related SAE (e.g. spontaneous abortion) or any other SAE experienced during pregnancy must be recorded on a separate SAE Report Form provided by Pharmacovigilance and reported to Pharmacovigilance as per SAE reporting procedures.

Abnormal pregnancy outcomes are considered SAEs and must be reported using the SAE Form. Investigators must actively follow-up, document and report to Sponsor the progress of the pregnancies until an outcome is reached. At the end of pregnancy, the Investigator will complete an End of Pregnancy Form provided by Pharmacovigilance and report it to Pharmacovigilance.

The outcome of all pregnancies (spontaneous miscarriage, elective termination, normal birth or congenital abnormality) must be followed up and documented even if the patient was discontinued from the study.

All reports of congenital abnormalities/birth defects are SAEs. Spontaneous miscarriages should also be reported and handled as SAEs. Elective abortions without complications should not be handled as AEs.

# 9.5. Reporting of individual SAEs and SUSARs by the Sponsor

Sponsor ensures that all reporting requirements and timelines for reporting, as defined in the applicable national law will be followed. will distribute all SUSAR to all principal Investigators, and to each Regulatory Agency. will forward each individual SAE to the coordinating investigator.

# 9.6. Periodic reporting on safety to principal investigators The Sponsor through ensures that the reporting requirements and timelines for reporting, as defined in the respective applicable laws, are followed. A Development Safety Update Report (DSUR) will be provided to the local investigators for filing into the investigator's file. will submit the DSUR to the involved ECs and involved Regulatory Agencies.

# 10. STATISTICS

# 10.1. Sample size calculation

# Sample size calculation:

The sample calculation has been done for the **initially proposed primary endpoint (cohort 1)** and it's based on a Fleming's Single Stage Procedure:

We want to show that the Intracranial response rate by modified RECIST 1.1 before local treatment is superior or equal to the reference value, say, 90=40%. Under the hypothesis to have a response rate under new treatment ( $\pi$ 1) of 60% with  $\alpha$  risk = 5% in one-sided test and a power of 80%, the required sample size is 38 patients.

Finally, assuming that, 20% of patients will be lost of follow up, die or progress before day 56 without doing the first tumour assessment (according data published in COMBI-MB study), the initial sample size will be 48 patients, to obtain 38 evaluable patients.

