## 4.1. Study Hypothesis

The main hypothesis is that:

 Intracranial response rate by modified RECIST 1.1 before local treatment will be ≥40% in cohort 1 and 2.

Study will be considered positive if the main hypothesis is achieved.

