#### 10.6. Statistical analysis

For each categorical variable, the results will be summarized by frequencies and percentages. For each continuous variable, the results will be summarized by descriptive statistics such as median, range, and interquartile range or by means, standard deviations and 95% confidence intervals (CIs). For proportions, point estimates and exact 95% confidence intervals will be calculated. For time to event endpoints, Kaplan-Meier estimates at selected time points and corresponding curves will be presented. Time to event is derived relative to the first study treatment administration. Laboratory values will be expressed as the absolute values and as grading (ordinal categorical variables) according to NCI CTCAE v 4.03.

Treatment-emergent AE (AEs starting after the administration of study treatment and up to study completion) will be summarized by system organ class and preferred term. Grading will be presented by type and grade in tables showing frequency and percentage of the within-patient worst grades. In addition, grade ≥3 AEs will be summarized separately. Full analysis details will be outlined in the statistical analysis plan (SAP).

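### Thirty-eight patients is what Fleming's approximation gives, but the exact one-sided 5% test at that size has 77.8% power, not 80%, and the plan states no responder cut-off

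*Combined protocol and SAP*

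**What the plan says.** Protocol section 10.1 and the statistical paragraph of the synopsis give the same calculation. Of the method, section 10.1 says "it's based on a Fleming's Single Stage Procedure". The aim is to show that the intracranial response rate "is superior or equal to the reference value, say, 90=40" per cent (the symbol for the null rate is garbled), with 60% as the alternative. The error rates and the result are given as "in one-sided test and a power of 80%, the required sample size is 38 patients". Allowing for 20% of patients without a first tumour assessment, "the initial sample size will be 48 patients, to obtain 38 evaluable patients". Section 10.1 ties this calculation to the cohort 1 endpoint that was proposed at the outset. The current primary endpoint (sections 3.0.1, 4.2 and 10.2) pools cohorts 1 and 2, with at least 63 patients planned.

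On what counts as success, section 4.1 states the hypothesis that the rate "before local treatment will be ≥40% in cohort 1 and 2", followed by "Study will be considered positive if the main hypothesis is achieved". On analysis, section 10.6 says "For proportions, point estimates and exact 95% confidence intervals will be calculated". Neither the protocol nor the SAP's primary efficacy tables give a number of responders, a test, or an interval bound that decides the primary endpoint.

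**The concern.** A single-arm phase II trial with a binary endpoint has a decision rule that is a whole number of responders. Its true error rates follow from that number. Here the number is missing, and the stated 80% power comes from a continuous approximation that no integer cut-off at 38 patients can match.

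The practical risk is a borderline result. Three thresholds can be drawn from the text: 16 of 38 from the wording of section 4.1, 21 of 38 from the one-sided 5% test in section 10.1, and 22 of 38 if someone judges success by the interval in section 10.6. Their type I errors run from 46% down to 1.9%. With 21 responders the trial would be positive by the stated test, yet a two-sided 95% interval would still include 40%. The plan does not say which reading governs. The operating characteristics for the pooled endpoint, which is now primary, are not stated at all.

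**Working it through.** **Inputs.** Null rate p0 = 0.40, alternative p1 = 0.60, one-sided level 5%, power 80%, 38 evaluable and 48 enrolled (section 10.1); at least 63 enrolled in all (synopsis). Two assumptions are mine: the 95% interval in section 10.6 is two-sided, and the 20% loss also applies to the pooled 63.

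**Reproducing the plan's figures.** The approximation is n = [(z0.95·√(p0q0) + z0.80·√(p1q1)) / (p1 − p0)]². Both variance terms equal 0.24, so n = [(1.645 + 0.842)·√0.24 / 0.20]² = 37.1, rounded up to 38. Approximate power at 38 is Φ(0.20·√38/√0.24 − 1.645) = Φ(0.87) = 80.8%. Enrolment is 38/0.80 = 47.5, rounded up to 48. All three agree with the plan.

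**Exact test at 38.** Let X be the number of responders.

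- P(X ≥ 20 | 0.40) = 7.8%, which exceeds 5%.
- P(X ≥ 21 | 0.40) = 4.1%, which is allowed.
- P(X ≥ 21 | 0.60) = 77.8%, the power.

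Fleming's own boundary leads to the same cut-off: 38 × 0.40 + 1.645·√(38 × 0.24) = 20.17, so at least 21. The gap to the stated power is 80 − 77.8 = 2.2 points. The smallest sample with exact power of at least 80% is 42 (cut-off 23, type I error 3.75%, power 80.3%).

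**The three readings at 38.**

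| Reading | Cut-off | Type I error | Power at 60% |
|---|---|---|---|
| Section 4.1 as a point estimate (0.40 × 38 = 15.2) | ≥16 | 45.6% | 99.2% |
| Section 10.1, exact one-sided 5% test | ≥21 | 4.1% | 77.8% |
| Section 10.6, if the lower limit of a two-sided exact 95% interval had to exceed 40% | ≥22 | 1.9% | 67.0% |

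Exact (Clopper-Pearson) lower limits show where the second and third part. At 21/38 the two-sided 95% limit is 38.3% and the one-sided 95% limit is 40.7%. At 22/38 the two-sided limit is 40.8%. The one-sided limit, which is the lower end of a two-sided 90% interval, agrees with the stated test.

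**Other sample sizes, with 60% response in the set analysed.**

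| Set | One-sided 5% rule | Type I error | Power |
|---|---|---|---|
| Cohort 1, all 48 | ≥26 | 3.3% | 83.5% |
| Pooled, 50 evaluable (63 × 0.80 = 50.4) | ≥27 | 3.1% | 84.4% |
| Pooled, all 63 | ≥33 | 3.1% | 91.3% |

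With the two-sided interval as the rule, power would be 76.6% at 50 (≥28) and 86.5% at 63 (≥34).

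**The case against.** The strongest reply is that nothing has been miscalculated. The protocol names Fleming's procedure, and the approximation gives 38. The 2.2-point gap is the ordinary difference between a normal approximation and an exact binomial. At this size exact power jumps by several points with one patient (77.8% at 38, 73.5% at 39, 79.1% at 40). The exact type I error of 4.1% respects the stated 5%. All of this stands, and the gap alone would be a minor note.

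A reader might also infer that the trial really runs at 67% power because the two-sided 95% interval is the planned analysis. The documents do not support that. Section 10.6 describes intervals for proportions in general. It does not say two-sided, does not name the primary endpoint, and does not require the lower limit to exceed 40%. The only testing language for this endpoint is the one-sided test in section 10.1. The 67.0% is therefore conditional on a rule that nobody has written down.

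Nor should a reader conclude that the current primary analysis is underpowered. The 38-patient calculation belongs to the earlier cohort 1 endpoint, and the pooled endpoint exceeds 80% under the protocol's 60%.

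The reply does not answer the missing rule. Without a cut-off, the success wording of section 4.1 can be taken literally, with the error rate shown above.

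**Conclusion.** The sample size is correctly derived, but the stated 80% power is not what the exact test delivers: at 38 patients it is 77.8%, with type I error 4.1% at a cut-off of 21. The shortfall is small. The more important gap is that no decision rule is written, so thresholds of 16, 21 and 22 of 38 can all be argued from the text.

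For the pooled primary endpoint, power is 84.4% with 50 evaluable patients and 91.3% with 63. Both figures assume a 60% response rate in both cohorts and in the set analysed. The SAP reports the main analysis in both the ITT and the PP population. If patients without an assessment count as non-responders in the ITT set, the rate there falls (60% × 0.80 = 48% with the plan's 20% loss) and the 91.3% no longer applies.

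**What to change.** No patients need to be added. The changes are to wording.

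1. In section 10.1 and the synopsis, keep 38 as the result of Fleming's approximation. Add that for the cohort 1 calculation success means at least 21 of 38, with exact one-sided type I error 4.1% and power 78%.
2. State the exact one-sided 5% rule for the current pooled endpoint, for the analysis set that decides it. Examples are at least 33 of 63 (type I error 3.1%, power 91.3%) and at least 27 of 50 if 20% are not evaluable (3.1%, 84.4%). Give the 60% assumption for both cohorts beside these figures.
3. In section 4.1, define success as rejection by that test, not as an observed rate of at least 40%.
4. In section 10.6 and the SAP response tables, report the exact one-sided 95% lower limit (two-sided 90% interval) beside the 95% interval, and say that the 95% interval is for estimation.
5. The SAP's treatment compliance section already refers to database closure. Label any cut-off added now as derived from the one-sided 5% test stated in the protocol, so that it is not mistaken for one fixed in advance.

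The cost is a revision of the text and a slightly less favourable stated power for cohort 1.

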#### 10.5. Definition of study populations

Data of study will be analysed in the following populations:

- 1. ITT: All patients that have been enrolled in the trial.
- 2. Evaluable population per protocol (PP): All patients fulfilling all eligibility criteria and having at least two valid tumour assessments (baseline and one evaluation MRI or CT-scan) without any protocol deviation that makes the patient invalid for the primary endpoint evaluation.
- 3. Safety population: All patients receiving at least one dose of treatment.

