# 3. RESULTS

# 3.1. RECRUITED PATIENTS

All baseline characteristics will be performed using the ITT and PP population. In order to report the main efficacy analysis, also both the ITT and PP population will be used, meanwhile the secondary efficacy endpoints will be analyzed using the PP population. Finally the safety population will be used to report the safety results.

Table 8: Patients recruited by Hospital

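### No sentence says whether ITT or PP decides the primary iORR, and SAP 3.1 assigns secondary efficacy to PP, a set that drops some patients because they died or progressed early

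*Combined protocol and SAP*

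**What the plan says.** Protocol 4.1 states the hypothesis as "Intracranial response rate by modified RECIST 1.1 before local treatment will be ≥40% in cohort 1 and 2" and adds: "Study will be considered positive if the main hypothesis is achieved". It names no population.

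Protocol 10.5 lists ITT (everyone enrolled), PP and safety sets without ranking them. PP is limited to eligible patients "having at least two valid tumour assessments (baseline and one evaluation MRI or CT-scan", and "without any protocol deviation that makes the patient invalid for the primary endpoint evaluation". SAP section 2 likewise requires a baseline and a first assessment for PP.

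Protocol 10.1 sizes cohort 1 for evaluable patients: it assumes that "20% of patients will be lost of follow up, die or progress before day 56 without doing the first tumour assessment", so "the initial sample size will be 48 patients, to obtain 38 evaluable patients".

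SAP 3.1 says: "In order to report the main efficacy analysis, also both the ITT and PP population will be used". SAP 4.1 (ITT) and 4.2 (PP) both carry the title of primary efficacy objective. SAP 3.1 continues that "the secondary efficacy endpoints will be analyzed using the PP population". The SAP nevertheless has ITT shells for response duration (Table 43), OS (4.5.1 to 4.5.3), iPFS (4.6.1 to 4.6.3) and ePFS (4.7.1 to 4.7.3).

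Protocol 10.7 bases the analysis on observed data without replacing missing values for dropouts. Protocol 10.2 defines iORR as a proportion of patients without saying how unassessed patients count.

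**The concern.** This is a single-arm trial with one positive-or-negative claim. Two unranked primary tables leave that claim undetermined whenever they disagree.

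The sets differ partly for reasons tied to outcome. A patient who dies or deteriorates before any scan stays in ITT but cannot enter PP. Removing such patients shrinks the denominator without removing responders, so the PP rate rises. The same selection raises PP OS, because entry to PP requires surviving to a scan. Exclusions for ineligibility or protocol deviation are different: they can move the estimate either way.

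For secondary endpoints, the sentence in SAP 3.1 makes the selected set the stated one and conflicts with the ITT tables that follow it.

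**Working it through.** **1. The plan's own figures.** Inputs from protocol 10.1: null 40%, alternative 60%, one-sided 5%, power 80%, 20% without a first assessment.

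n = [(1.645·√(0.4·0.6) + 0.842·√(0.6·0.4)) / 0.2]² = 37.1, rounded up to 38. Inflated: 38/(1 − 0.20) = 47.5, rounded up to 48. Both figures reproduce. The 38 are evaluable patients, so the sizing leans towards PP without saying that PP decides.

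**2. Model for the current primary.** The primary pools both cohorts (protocol 3.0.1, 4.1, 4.2, 10.2), so N = 48 + 15 = 63. My assumptions:
- a fixed number u unassessed, all non-responders in ITT and all excluded from PP, so that PP has m = 63 − u;
- responders X ~ Binomial(m, 0.60);
- success if X reaches the smallest r with P(X ≥ r | n, 0.40) ≤ 0.05.

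For ITT this gives 33/63 (exact alpha 0.031). PP passes and ITT fails when r_PP ≤ X ≤ 32. On the literal reading of 4.1 (observed rate at least 40%), ITT needs 26/63, since 0.4 × 63 = 25.2, and the split is r_PP ≤ X ≤ 25.

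| u | m | r_PP, exact test | PP passes, ITT fails | r_PP, literal 40% | PP passes, ITT fails |
|---|---|---|---|---|---|
| 2 | 61 | 32 | 5% | 25 | 0.1% |
| 5 | 58 | 30 | 19% | 24 | 0.5% |
| 7 | 56 | 29 | 30% | 23 | 1.3% |
| 10 | 53 | 28 | 46% | 22 | 4% |
| 13 | 50 | 27 | 61% | 20 | 10% |

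Ten is the planned loss in cohort 1 alone (48 − 38). Thirteen adds an assumed 3 of 15 in cohort 2, for which the documents give no figure.

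**3. Cohort 1 alone (N=48, now a secondary endpoint), 10 unassessed.** PP needs 21/38 and ITT 26/48, so 21 to 25 responders split the verdict: P(21 ≤ X ≤ 25 | 38, 0.60) = 59%. On the literal reading (16/38 against 20/48) it is 13%. If 5 of the 10 stay in PP as not evaluable, PP needs 24/43 and the exact-test figure falls to P(24 ≤ X ≤ 25 | 38, 0.60) = 23%. If 8 stay, PP needs 25/46 and it is P(X = 25 | 38, 0.60) = 10%.

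**4. Cohort 1 power in ITT.** If 60% refers to assessed patients and 20% are unassessed, power is P(X ≥ 26 | 38, 0.60) = 19% with exactly 10 unassessed, or P(X ≥ 26 | 48, 0.48) = 24% if the number varies (0.8 × 0.60 = 0.48). If 60% refers to all enrolled, it is P(X ≥ 26 | 48, 0.60) = 83.5%. Protocol 10.1 does not say which is meant.

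**5. OS.** If d of 48 die before the first scan and nobody else is excluded, PP survival at later times is ITT survival times 48/(48 − d): 1.04, 1.12 and 1.26 for d = 2, 5 and 10. The last is the extreme in which every planned unassessed patient has died.

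**The case against.** **PP is implied.** The sizing on evaluable patients, and the PP clause on deviations that affect the primary endpoint, could be taken to show that PP decides. Neither is a decision rule, and SAP 3.1 does not adopt one. Intending PP would also have a cost: if the all-enrolled rate in cohort 1 were exactly 40% with 20% unassessed (50% among assessed), PP would pass with probability P(X ≥ 21 | 38, 0.50) = 31%.

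**The size can be overstated.** A reader might take 59% as the chance that the trial's verdict flips. The documents do not support that. It is for cohort 1, no longer the primary; it uses cut-offs the plan does not contain; and it assumes no unassessed patient enters PP. The PP shells in SAP 4.2 have rows for not-evaluable patients, and protocol 10.5 accepts a CT scan, so someone with a body CT but no brain MRI can be in PP. Unscheduled imaging is allowed, so early progression seen on a scan need not exclude a patient. These objections stand. The 20% is also a planning figure, not split by cause.

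**Secondary results on PP only.** A reader might infer this from SAP 3.1. It is not so: the ITT tables are planned. What stands is the contradiction.

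**ITT already counts unassessed patients as failures.** The ITT definition and Table 40's not-evaluable row and total point that way. But Table 40 lists not evaluable apart from stable or progressive disease, and protocol 10.7's observed-data rule pulls the other way. A rule is needed.

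**Both sets are reported in an uncontrolled phase II trial.** This limits the harm because readers can see both results. It does not say which one makes the study positive.

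**Conclusion.** The point holds in this form: no text ranks ITT and PP for the primary, PP selects partly on early death or progression, and SAP 3.1 contradicts the SAP's own shells on secondary efficacy. PP response and OS are biased upward to the extent that exclusions are early failures; for other exclusions the direction is unknown.

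The tabulated risks of opposite verdicts on the pooled primary are upper bounds, and their size depends mainly on the success rule: substantial under an exact test, small if 4.1 means an observed 40%. The documents do not settle that rule or give the actual number unassessed. This should be fixed, but it does not show that the trial's conclusion is wrong.

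**What to change.** 1. In protocol 10.5 and SAP 3.1, make ITT decisive for iORR, with not-evaluable or unassessed patients kept in the denominator as non-responders, and PP as sensitivity. State in 10.7 that the observed-data rule does not remove them.
2. In SAP 3.1, change the secondary efficacy population to ITT, matching the existing shells, with PP as sensitivity.
3. In protocol 10.1, state which patients the 40% and 60% refer to, and restate power for that set.
4. Disclose when the deciding set was chosen and report both sets. The SAP appears to have been written after database closure: 3.5 reports patients still on treatment at closure, and 4.6.1 gives a count of censored patients.

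No new data are needed, and the main ITT tables already exist. The cost is a headline response rate that is likely to be lower than in PP, and an openly late specification.
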